3.1 General Design

This is an open label, human study evaluating the safety and tolerability, feasibility, and efficacy, s of PRP applied in topical fashion intra-operatively during RP. Subjects will be screened at outpatient clinic visit appointments and interested qualified subjects will be

consented and offered participation in this trial. The study aims to enroll 20 men with newly diagnosed prostatic adenocarcinoma that are planning to undergo bilateral nerve-sparing RP. Once written consent has been obtained baseline functional and laboratory assessments will be obtained and patients will be followed for the expected duration for study participation of 18 months.

Since the present study is a single-arm study, evaluation of safety and efficacy parameters will have to be performed using benchmark outcomes from historical controls. At Mayo Clinic, all patients undergoing RP are included in the Mayo Clinic Prostatectomy Registry. The prostatectomy registry is prospectively maintained by study nurses. The prostatectomy registry maintains detailed oncologic and quality of life data using PSA testing and the same validated questionnaires proposed by the current study. The comparator for the present study would be other subjects from the Mayo Clinic Prostatectomy Registry that underwent bilateral nervesparing RP within the same study dates and met all of the other inclusion and exclusion criteria for the present study but did not have PRP applied intraoperatively to the neurovascular bundles.

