4.2 Exclusion Criteria

- Unable or unwilling to provide informed consent
- Vulnerable study populations
- Active systemic infection
- Diabetes Mellitus diagnosis
- Preexisting ED or urinary incontinence
- Metastatic or locally advanced prostatic adenocarcinoma on preoperative evaluation
- Men found grossly or pathologically to have locally advanced or metastatic disease at the time of RP
- An estimated blood loss of >750 mL at the time of RP
- Treatment prior to surgery with any form of hormones, antiandrogens or androgen deprivation therapy
- Use of an antidepressant, beta blocker or ED medication at the time of study
- Screening Men without a regular sexual partner
- Use of aspirin or heparin 2 weeks before RP
- Need for use of aspirin or heparin for 2 weeks or more after RP.

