4.3 Subject Recruitment, Enrollment and Screening

Subjects will be recruited for the study in the outpatient clinic environment by the PI and Co-Investigators. Identified subjects will discuss the study with a Study Coordinator. At that time, the inclusion and exclusion criteria will be discussed as well as the rationale, the potential benefits, and potential risks associated with the study. The recruitment, enrollment, and screening procedures will occur in the outpatient clinic setting. If subjects want to proceed with the study, informed consent will be obtained by the study coordinator or investigator.

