5.4.1 Specifics of PRP Sample Preparation

To prepare the sample, **180** mL of whole blood will be obtained from the patient by venipuncture during the RP by Anesthesia personnel. The whole blood will be placed in the platelet concentration device and centrifuged following manufacturer's instructions. After final processing, the final PRP sample will consist of 10 mL of product that will be used for intraoperative application. The PRP created intra-operatively would be placed into a syringe labeled "PRP." Samples of whole blood and PRP will also be sent to the laboratory for analysis for quality control purposes, in accordance with Division of Laboratory Medicine SOP. ¹⁰

During the RP procedure, PRP will be applied to the NVB after completion of the vesicourethral anastomosis and after conventional techniques have been performed to achieve adequate hemostasis. Conventional techniques for hemostasis include the placement of surgical clips or suture as required to bleeding sites on the neurovascular bundle. No additional hemostatic products will be applied to the neurovascular bundles during the study. PRP will be applied evenly to the entire length of the NVB by mechanical transfer of product. For robotic procedures, a laparoscopic spoon instrument will be used to deliver the PRP directly to the NVB. For open procedures, delivery of PRP will occur via PRP-labelled syringe. After application of PRP, the surgical team will then complete RP in standard fashion.

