8.6 Medical Monitoring

It is the responsibility of the PI to oversee the safety of the study at his/her site. This safety monitoring will include careful assessment and appropriate reporting of adverse events as noted above, as well as the construction and implementation of a site data and safety-monitoring plan (see section 10 "Study Monitoring, Auditing, and Inspecting"). Medical monitoring will include a regular assessment of the number and type of serious adverse events.

Since the present study is a single-arm study, evaluation of safety and efficacy parameters will also be performed using benchmark outcomes from historical controls. At Mayo Clinic, all patients undergoing RP are included in the Mayo Clinic Prostatectomy Registry. The prostatectomy registry is prospectively maintained by study nurses. The prostatectomy registry maintains detailed oncologic and quality of life data using PSA testing and using the same validated questionnaires proposed by the current study. By using other subjects from the Mayo Clinic Prostatectomy Registry that underwent bilateral nerve-sparing RP within the same study dates (and those that met all of the other inclusion and exclusion criteria for the present study but did not have PRP applied intraoperatively to the neurovascular bundles), another means to compare the safety and preliminary evidence of efficacy will be achieved.

9 Data Handling and Record Keeping

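### Nothing in the plan ensures or checks that the registry comparator resembles the PRP men on operating surgeon or on open versus robotic approach

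*Combined protocol and SAP*

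**What the plan says.** The trial has a single arm. Section 3.1 states that "evaluation of safety and efficacy parameters will have to be performed using benchmark outcomes from historical controls". It takes the comparator from the institution's prostatectomy registry, noting that "all patients undergoing RP are included in the Mayo Clinic Prostatectomy Registry". Comparators are men without PRP who "underwent bilateral nervesparing RP within the same study dates and met all of the other inclusion and exclusion criteria for the present study". Section 8.6 repeats this rule and says of it that "another means to compare the safety and preliminary evidence of efficacy will be achieved".

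For the PRP arm, section 3.1 describes men who are screened in clinic, qualify, are interested and consent. Section 4.3 adds: "Subjects will be recruited for the study in the outpatient clinic environment by the PI and Co-Investigators". Both surgical approaches are permitted, with different delivery of the product. Section 5.4.1 says "For robotic procedures, a laparoscopic spoon instrument will be used to deliver the PRP directly to the NVB" and specifies a syringe for open procedures.

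Section 7.2 plans univariate description and temporal trends. It does not mention the registry comparison, and no section mentions matching, stratification or adjustment.

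**The concern.** The comparator rule controls patient case mix but is silent on who operated and by which approach. The two groups also come from different sources: one is recruited by the investigators from willing men, and the other is drawn from all of the institution's prostatectomy patients. If outcomes differ between surgeons or approaches and the mix differs between groups, that difference will be read as an effect of PRP.

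Two objectives are exposed. Safety and tolerability form the primary objective, and section 3.1 makes the registry the benchmark for them. Preliminary efficacy is secondary, but the registry is its only external reference. Leaving out a p-value does not help, because a biased benchmark stays biased in a purely descriptive table.

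The rule is also hard to apply as written. It calls the men historical controls but selects them from the trial's own dates. It also invokes the trial's exclusion criteria without saying how one that concerns consent to this study applies to men who may never have been asked.

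**Working it through.** **1. Who can enter each group.** Under section 4.4.1 a consenting man receives PRP unless he is withdrawn during surgery for blood loss above 750 mL or for locally advanced or metastatic disease. Section 4.2 lists both as exclusions, so such men drop out of the comparator too. The text leaves these routes into the comparator for an eligible man without PRP:

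- he was not approached (no section requires every eligible man to be approached);
- he declined;
- he withdrew voluntarily before surgery;
- he was operated on after enrolment closed, if the date window runs that far.

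The first and last routes can include the trial surgeons' own patients. The second depends on how one reads the exclusion "Unable or unwilling to provide informed consent".

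**2. What the rule holds fixed.**

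| Factor | Fixed by the rule? | Source |
|---|---|---|
| Institution, bilateral nerve-sparing surgery | Yes | 3.1 |
| Age 50-60, SHIM >19, normal continence, regular partner | Yes | 4.1 |
| No diabetes, listed drugs, advanced disease or blood loss >750 mL | Yes | 4.2 |
| Operating surgeon | No | not mentioned in 3.1 or 8.6 |
| Open or robotic approach | No | both allowed, 5.4.1 |
| Willingness to take part | No | 3.1, 4.3; consent criterion unclear |
| Calendar window | Undefined | 3.1, 8.6 |

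The Study Summary gives 18 months both for the whole study and for each man's participation, so it does not settle the window.

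**3. Repair elsewhere.** Sections 7.1 to 7.3 give the sample of 20, the descriptive methods and the analysis population. None of them addresses the comparison.

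**4. Size.** The plan prints no figure to reproduce and no outcome rates by surgeon or approach, so every rate here is an assumption. Let all PRP men be patients of trial surgeons, who achieve recovery rate p_T. Let other surgeons achieve p_O, let a share s of controls come from trial surgeons, and let PRP have no effect. The apparent difference is

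D = p_T − [s·p_T + (1 − s)·p_O] = (1 − s)(p_T − p_O).

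| p_T | p_O | s | D |
|---|---|---|---|
| 60% | 50% | 0 | 10 points |
| 60% | 40% | 0 | 20 points |
| 60% | 50% | 0.5 | 5 points |
| 60% | 40% | 0.5 | 10 points |

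The sign reverses if the other surgeons do better, and D is zero if s = 1 or the rates are equal. The number of controls does not enter the formula, so a larger registry pool does not remove the bias. Approach works the same way: D is the difference in share times the outcome gap. For example, an assumed 40-point difference in robotic share and a 20-point outcome gap give 0.40 × 20 = 8 points.

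**5. Scale.** If 10 of 20 PRP men recover, the exact (Clopper-Pearson) 95% interval is 27.2% to 72.8%, about 23 points either side. Sampling error is therefore large. The interval makes no allowance for D, which is added to it.

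**The case against.** The rule already restricts case mix heavily: one institution, a ten-year age band, normal baseline function, and no diabetes, advanced disease or high blood loss. The study is small and descriptive, efficacy is called preliminary, and no decision rule rests on the comparison. Section 8.6 also puts the benchmark more softly than section 3.1, saying that "evaluation of safety and efficacy parameters will also be performed using benchmark outcomes from historical controls". All of this stands, and it limits the stakes. It does not fill the gap, because none of those restrictions acts on surgeon or approach.

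A reader might infer more than the documents support:

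- **Surgeon is confounded with PRP by construction.** No section names the participating surgeons or says that any surgeon stays out. Trial surgeons' own patients can be comparators if they were not approached or were operated on after enrolment closed.
- **The consent exclusion removes decliners and leaves only unapproached men.** The willingness of unapproached men is equally undocumented. Read sensibly, a trial-consent criterion does not apply to registry men at all. This calls for clarification and is not evidence of bias.
- **The Background shows that erectile outcome depends on the surgeon.** Section 1.1 calls the cause multifactorial and lists thermal or mechanical trauma among common factors. Dependence on the operator is plausible but not stated.
- **Approach mix would shift the transfusion benchmark.** Section 1.5 gives <1 to 5% for prostatectomy and does not tie that range to approach.
- **The same surgeons' pre-trial patients would be the cleanest controls.** They would bring calendar drift, so using them is a trade-off.

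**Conclusion.** The point holds as a missing safeguard. As planned, a PRP-versus-registry difference cannot be separated from differences in surgeon, approach or willingness to take part, and the plan does not ask for the data that would show whether such differences exist.

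It does not show that the groups are imbalanced. The documents give no surgeon or approach distribution for either group, so the size and direction of any bias are unknown. The 5-20 points rest wholly on assumed recovery rates of 60% against 40-50% and on half or all of the controls coming from other surgeons. The trial can proceed. This is a cheap improvement to a benchmark that bears on the primary safety objective and on preliminary efficacy.

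**What to change.** In sections 3.1 and 8.6:

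1. Restrict registry comparators to patients of surgeons who apply PRP in the trial.
2. Match on open versus robotic approach, or report results by approach, and by surgeon where numbers allow.
3. Report the surgeon and approach mix of both groups.
4. Label the comparison descriptive.
5. Give start and end dates for the comparator window, and reconcile the historical label with the concurrent definition.
6. State that the trial-consent criterion is not applied to registry men.

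Section 7.2 should then point to this comparison.

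The cost is protocol wording and a registry query; no patients, visits or procedures are added. The control pool will be smaller, and with 20 PRP men the strata will be sparse, so results by surgeon may be no more than a listing. The fix requires that surgeon and approach can be obtained from the registry or operative records, which the documents do not state. Volunteer selection is not removed, which is a further reason for the descriptive label.

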4.4 Early Withdrawal of Subjects

4.4.1 When and How to Withdraw Subjects

A subject may withdraw at any time prior to RP. There are no adverse safety considerations in the study for those deciding to withdraw from the study. Subjects may choose to discontinue study participation after RP surgery and will be counted as withdrawn

A subject consenting to the study will receive PRP at the time of RP unless the surgical team decides intra-operatively to withdraw a subject from the study in the following situations:

- Estimated blood loss greater than 750 mL
- Evidence of disease grossly and/or pathologically that the prostate cancer is locally advanced or metastatic

• Documentation of the reason for withdrawal will be retained in the study files.

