4.4.2 Data Collection and Follow-up for Withdrawn Subjects

As part of normal clinical care, subjects that have withdrawn from the study will still have routine postoperative monitoring after RP. Any collected study data from withdrawn subjects will not be included in the data analysis. Since all patients have their outcomes tracked after RP at Mayo Clinic, postoperative data would be available should this be needed as part of another study protocol.

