5.6 Prior and Concomitant Therapy

The following concomitant medicines are not permitted during the study:

- Any type of androgen deprivation therapy
- Aspirin and heparin for 2 weeks before or 2 weeks after the date of PRP application
- Use of an antidepressant, beta blocker or ED medication at the time of study screening

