7.3 Subject Population(s) for Analysis

Data from all subjects consented for the study and completing postoperative visits will be evaluated.

² Vitals will be abstracted from the medical record for visit 3, post-operative day 2

³ Week 1 and week 12 visits may be done on-site or via telephone interview or email. Physical exam and vitals will be performed for these visits if participant is able to return to Mayo Clinic. Outside records for physical exam and vitals will be requested if visits are done remotely.

⁴ The 6, 9, 12 and 18 Month visits may be done remotely via telephone interview or email. Completed SHIM/EPIC Questionnaires may be returned to study site by mail, email or fax. PSA testing: A local clinic may be used for venipuncture, using mail in lab kit for sample return to Mayo Clinic. PSA testing window for week 12 and 6, 9, 12, 18 month visit is +/- 21d

8 Safety and Adverse Events

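### The registry control definition carries over a post-operative aspirin/heparin criterion with no rule on when it is judged, so the safety comparison may be selected on a consequence of a safety event

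*Combined protocol and SAP*

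**What the plan says.** Section 3.1 explains that, with a single arm, "evaluation of safety and efficacy parameters will have to be performed using benchmark outcomes from historical controls". The comparator is registry men operated on within the study dates who "met all of the other inclusion and exclusion criteria for the present study but did not have PRP applied intraoperatively to the neurovascular bundles". Section 8.6 repeats this definition and says that through it "another means to compare the safety and preliminary evidence of efficacy will be achieved". Neither section sets aside criteria that depend on what happens after the operation.

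Section 4.2 contains such a criterion: "Need for use of aspirin or heparin for 2 weeks or more after RP". It does not say whether the need is the one foreseen before surgery or the one that actually arose.

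For trial men, the schedule in Section 6.8 marks eligibility review at screening only. Under Section 4.4.1 a consented man receives PRP "unless the surgical team decides intra-operatively to withdraw a subject from the study in the following situations". The two situations are blood loss above 750 mL and locally advanced or metastatic disease. A man may also choose to leave after surgery. Section 4.4.2 adds: "Any collected study data from withdrawn subjects will not be included in the data analysis". Section 4.4.3 replaces withdrawn men until 20 have completed 18 months. Section 7.3 defines the analysis set: "Data from all subjects consented for the study and completing postoperative visits will be evaluated". It has no exclusion for later aspirin or heparin.

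**The concern.** A control's chart is read after the outcome is known. If the Section 4.2 criterion is applied to recorded use, a control can be removed because a post-operative complication was treated with heparin or aspirin for at least 14 days. A venous thrombosis or a cardiac event would be an example. That is selection on a consequence of a safety outcome. The PRP men are chosen before surgery, and nothing in the plan says what happens to one who meets the criterion later.

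The stake is the primary objective. If PRP men with such events stay in while the matching controls are dropped, PRP looks worse than it is. If the PRP men are withdrawn, their complications leave the analysis that is meant to detect them. Enrolling more controls removes neither problem, because the error lies in who is allowed to be counted.

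**Working it through.** **Inputs from the documents.** N = 20, single arm (Section 7.1). No error rate, power, margin or number of controls is stated, so there is no planned figure to reproduce. The criterion starts at 2 weeks, that is, 14 days. The documents give no rate for events treated in this way.

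**Assumed inputs.** A common true event rate p of 1% to 5% in both groups. A share f of control events, 25% to 100%, that meet the criterion and are removed. For step 4 only, 60 controls.

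**Step 1. What the text allows.** Two points are open: how the criterion is judged in controls, and what happens to a PRP man who meets it later.

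| Controls judged on | PRP man kept | PRP man withdrawn |
|---|---|---|
| Need foreseen before surgery | Events counted in both groups | Events lost in PRP men only; PRP looks safer |
| Actual post-operative use | Events lost in controls only; PRP looks worse | Events lost in both; the comparison is silent on them |

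Only one of the four cells gives a sound safety comparison, and the plan does not say which cell applies.

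**Step 2. Events lost in controls only.** Removing men removes them from numerator and denominator, so the control rate becomes c = p(1 − f)/(1 − pf). For p = 2% and f = 50%: c = 0.02 × 0.5/(1 − 0.01) = 0.0101, a false excess of 0.99 points.

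| p | f = 25%: c (excess, points) | f = 50%: c (excess, points) | f = 100%: c (excess, points) |
|---|---|---|---|
| 1% | 0.75% (0.25) | 0.50% (0.50) | 0 (1.0) |
| 2% | 1.51% (0.49) | 1.01% (0.99) | 0 (2.0) |
| 3% | 2.27% (0.73) | 1.52% (1.48) | 0 (3.0) |
| 5% | 3.80% (1.20) | 2.56% (2.44) | 0 (5.0) |

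The apparent risk ratio p/c is about 1.3 at f = 25% and about 2 at f = 50%, with no true difference.

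**Step 3. Sampling error with 20 men.** One event is 1/20 = 5%, exact (Clopper-Pearson) 95% CI 0.1% to 25%. With no events, the one-sided 95% upper limit is 1 − 0.05^(1/20) = 13.9%. Every excess in step 2 is smaller than this uncertainty.

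**Step 4. How often the rule itself produces an event-versus-none picture.** Take events that all meet the criterion (f = 100%). The chance of at least one in 20 PRP men is 1 − (1 − p)^20. With the rule, controls show none. Without it, 60 controls would show none with probability (1 − p)^60.

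| p | At least 1 in 20 PRP men | None in 60 unselected controls | Both by chance, without the rule | Added by the rule |
|---|---|---|---|---|
| 1% | 18% | 55% | 10% | 8 points |
| 2% | 33% | 30% | 10% | 23 points |
| 3% | 46% | 16% | 7% | 38 points |

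At 1%, more than half of these pictures would arise by chance anyway. At 2% and 3%, most come from the rule.

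**The case against.** **The criterion is in the trial men's own list.** On paper it applies to both groups. This stands: the asymmetry comes from unstated handling, not from a rule aimed at controls alone. It does not clear the plan, because enforcing the criterion on treated men by withdrawal deletes their events.

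**Need may mean foreseen need.** Eligibility review is marked at screening only, and on that reading a control who later has a clot stays in. This is a fair reading. However, Section 4.2 also holds criteria settled at the operation, so it is not purely a screening list, and the text does not choose.

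**No clotting or bleeding contrast is specified.** The methods in Section 7.2 are descriptive. The Study Summary names perioperative complications, length of stay and transfusion, but not clots or cardiac events. Section 3.1 describes the registry as holding oncologic and quality-of-life data. This limits the claim to a possible bias.

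**A stronger reading on exposure.** Section 5.6 lists as not permitted "Aspirin and heparin for 2 weeks before or 2 weeks after the date of PRP application", while Section 4.2 excludes only use of 2 weeks or more. A reader might infer that controls can carry 1 to 13 days of exposure that trial men cannot, so that the bleeding comparison flatters PRP. The documents do not support this as a finding. The two sections already disagree for trial men, and Section 5.6 can, less naturally, be read as barring a two-week course. Compliance monitoring is marked not applicable (Section 5.5), and actual use is unknown in both groups.

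**Conclusion.** The point holds as a gap in definition that may bias the safety comparison for one class of event: complications treated with aspirin or heparin for at least 14 days. The direction depends on handling that the plan leaves open.

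A reader might go further and say that every control treated for a clot or cardiac event is removed by rule, so that the control rate is zero by construction. That is too strong. It requires judging need on actual use, and even then it reaches only events treated with these two drugs for 14 days or more. To say that all such events are lost is true by definition and does not measure the effect on complications overall.

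The size cannot be set from the documents. Under the assumed rates and shares the false excess is 0.25 to 5 points, probably small beside the sampling error in 20 men. It is still worth correcting: it is systematic, it touches the primary objective, and it can be removed before controls are selected.

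**What to change.** - **Sections 3.1 and 8.6:** apply to registry controls only the Section 4.2 criteria that can be judged by the end of the operation. Do not exclude a control because aspirin or heparin was started later to treat a post-operative event.
- **Sections 4.4.2, 4.4.3 and 7.3:** keep every PRP-treated man in the safety analysis even if he later meets this criterion, and count such events in both groups. Recruiting a replacement should not remove the treated man from the safety set. Section 9.1 already lets the investigator use information collected before authorization is revoked.
- **Sections 4.2 and 5.6:** reconcile what they say about post-operative aspirin and heparin. Which medication rule is right is a clinical matter and is not judged here.
- **Reporting:** where the chart allows, describe actual aspirin and heparin use in both groups as a limitation. Do not restrict the main comparison by it: the registry is not shown to hold medication data, and restriction would shrink the control group.

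The cost is a sentence or so in each section. The safety denominator may exceed 20 if treated men are replaced. Control complications must be taken from the registry or chart, which the comparison in Section 8.6 needs in any case.
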